2.1 Primary Objective

To identify factors associated with the coincidence (concordance) between EUS diagnosis and pathological diagnosis for colorectal subepithelial lesions.

3. Endpoints

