6.4 Data Collection Items

1. Demographics: age, sex, initials;
2. Lesion location and size (maximum diameter);
3. EUS echogenic features, layer-related characteristics, EUS diagnosis (primary diagnosis), operator, and device information;
4. Pathology acquisition method, pathological layer, and pathological diagnosis.

7. Criteria for Study Termination / Suspension

7.1 The sponsor has the right to terminate or suspend the study. Before termination/suspension, the sponsor must notify the investigator, the ethics committee, and relevant regulatory authorities and provide the rationale. If the study is terminated/suspended early, restarting the study requires ethics committee approval.

7.2 Termination or suspension as required by the ethics committee.

8. Study Completion

The study will be completed when data collection reaches the predefined time interval.

9. Data Management

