10.1 Sample Size Determination

This is a single-center, retrospective, observational study. One-way analysis of variance (ANOVA) will be used to explore factors associated with concordance versus non-concordance between EUS diagnosis and pathological diagnosis. Using G*Power (version 3.1.9.7) with an effect size of 0.25, $\alpha = 0.05$, power $(1-\beta) = 0.80$, 10 predictors, and 2 groups, the required sample size was calculated to be 269 cases.

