10.3 Statistical Software and General Requirements

- Statistical analyses will be performed using SPSS.
- Continuous variables will be summarized using mean, standard deviation, median, minimum, and maximum values.
- Categorical variables will be summarized using frequencies and percentages.
- One-way ANOVA will be used to evaluate differences in potential factors between the concordant and non-concordant groups.
- Multivariable logistic regression will be performed to identify key factors independently associated with diagnostic concordance.

11. Study Management

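### The multivariable logistic model in 10.3 would be modestly and cheaply improved by Firth estimation, or at least by likelihood-ratio rather than Wald tests; the gain is small at the plan's 10 predictors

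*Combined protocol and SAP*

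**What the plan says.** The study has one objective, in section 2.1: "To identify factors associated with the coincidence (concordance) between EUS diagnosis and pathological diagnosis for colorectal subepithelial lesions". Section 10.3 gives it two analyses. The first is unadjusted: "One-way ANOVA will be used to evaluate differences in potential factors between the concordant and non-concordant groups". The second is the adjusted model: "Multivariable logistic regression will be performed to identify key factors independently associated with diagnostic concordance". The software is fixed in the same list: "Statistical analyses will be performed using SPSS". Nothing is said about the estimator, the test for each factor, or what happens if a factor level separates the outcome.

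Section 10.1 sets the planned size: "10 predictors, and 2 groups, the required sample size was calculated to be 269 cases". Section 8 ends the study by calendar rather than by count ("The study will be completed when data collection reaches the predefined time interval"), so the achieved number may differ from 269. Section 6.4 lists the candidate factors. Besides age, sex, location and size these include "EUS echogenic features, layer-related characteristics, EUS diagnosis (primary diagnosis), operator, and device information" and, from pathology, "Pathology acquisition method, pathological layer, and pathological diagnosis". No level counts are given. Section 1 cites EUS accuracy of roughly 43%-79% for gastrointestinal lesions in general; the plan gives no concordance rate for its own population.

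**The concern.** ML logistic regression exaggerates effects when the smaller outcome class is thin relative to the number of coefficients, and it gives an infinite estimate when a level contains only one outcome. When an estimate is very large or infinite, its standard error grows faster than the estimate and the Wald statistic collapses, so a strong factor can look non-significant. Several items in 6.4 probably have more than two levels, so 10 predictors could mean well over 10 coefficients. A layer or EUS diagnosis that is almost always called correctly is also the kind of factor this study is looking for. At stake is which factors are reported as independently associated with concordance, and how large their effects appear.

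**Working it through.** **The plan's own figure.** With the effect size of 0.25 read as Cohen's f, the noncentrality is N × f². At N = 269 this is 269 × 0.0625 = 16.8. An F-test at α = 0.05 with 10 numerator and N − 2 = 267 denominator degrees of freedom then has power 0.8003, so 269 reproduces. It sizes an F-test and says nothing about the logistic model.

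**Smaller outcome class.** N × min(c, 1 − c), with c the concordance assumed from section 1:
- c = 79%: 269 × 0.21 = 56.5, or 5.6 per predictor for 10 predictors
- c = 43%: 269 × 0.43 = 115.7, or 11.6
- c = 50% (maximum): 269 / 2 = 134.5, or 13.4

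**Number of coefficients (assumed).** Age, size and sex take one each. Seven items from 6.4 have L levels each (pathological layer and pathological diagnosis left out), giving 3 + 7 × (L − 1) = 10, 17, 24 and 31 for L = 2 to 5. At 79% concordance and 31 coefficients the smaller class has 56.5 / 31 = 1.8 lesions per coefficient.

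**Estimation.** Simulation with N = 269, 79% concordance, one true log-odds ratio of 0.50 per SD, all factors entered and 600 datasets per cell. Ranges cover level shares that are equal or fall by a factor of 0.7 or 0.5 per level. Divergence means any coefficient above 8 in absolute value.

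| Coefficients | ML median | Excess over 0.50 | ML divergence | RMSE, ML | RMSE, Firth |
|---|---|---|---|---|---|
| 10 | 0.525-0.542 | 5%-8% | 0% | 0.174-0.185 | 0.161-0.171 |
| 17 | 0.536-0.554 | 7%-11% | 0% | 0.178-0.192 | 0.157-0.164 |
| 24 | 0.552-0.578 | 10%-16% | 0%-18% | 0.194-0.217 | 0.160-0.179 |
| 31 | 0.583-0.605 | 17%-21% | 0%-77% | 0.225-0.235 | 0.171-0.175 |

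Firth medians were 0.49-0.51 and none diverged. The RMSE reduction is 1 − 0.161/0.174 = 7% at 10 coefficients, 1 − 0.157/0.178 = 12% at 17 and 1 − 0.175/0.235 = 26% at 31. A separate run gave 7% at 10 (0.157 vs 0.169) and 19% at 31 (0.183 vs 0.226). At 43%-50% concordance and 10 coefficients the ML median was 0.513-0.524, an excess of 3%-5%.

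**False positives at 17-31 coefficients, 79% (nominal 5%).** ML likelihood-ratio (LR) 5.8%-10.2%, Wald 4.5%-6.5%, Firth 3.9%-5.1%. A different set of designs with 20 coefficients, at 43%-79% concordance, showed milder LR inflation (4.7%-6.9%).

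**Power for a small, nearly always concordant level.** N = 269. In the 38-lesion example (log-odds ratio 2.0, 79% overall), that level is about 96% concordant against 76% elsewhere.

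| Setting | Wald | Firth | LR | Infinite ML estimate |
|---|---|---|---|---|
| 79%, 10 coefficients, 38 lesions, 2.0 | 65% | 90% | 93% | 22% |
| 79%, 17 coefficients, 38 lesions, 2.0 | 50% | 83% | 88% | 20% |
| 79%, 10 coefficients, 38 lesions, 1.5 | 61% | 72% | 78% | – |
| 79%, 17 coefficients, 38 lesions, 1.5 | 42% | 62% | 72% | – |
| 65%, 17 coefficients, 2.0 | 94% | 97% | 98% | – |
| 43%-50%, 2.0 | 99%-100% | 99%-100% | 99%-100% | – |

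Repeat runs of the first row gave Wald 67%-68.5%, Firth 89%-92% and LR 93%-94.5%. The second row depends on coding: with other level structures it was 69% / 89%-90% / 92%-94%. The Wald deficit against Firth at log-odds ratio 2.0 is therefore about 20-33 points. For a level with low concordance (log-odds ratio −2.0, 38 lesions) all three tests had power 0.998.

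**The planned ANOVA in the same situation (10 coefficients).** For the 38-lesion level with log-odds ratio 2.0, ANOVA detected the factor in 88%-91% of datasets and Firth in 89%-92%. At 1.5 both gave 74%. With 27 lesions and 2.0 they gave 77% and 78%.

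**The case against.** A reader might infer that the plan would miss a real factor in a third to a half of studies, or that its model would usually fail to converge. The documents support neither.

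- Section 2.1 asks for associated factors, and 10.3 also assigns that question to ANOVA, which flags the example factor about as often as Firth. What is at risk is only the conclusion of independent association, and only if Wald tests are used, which the plan does not say.
- The 77% divergence needs seven items at five levels each with the steepest shares, so that each has a level of about 9 lesions. With milder shares it is 5%, with equal shares 0%. Section 10.1 speaks of 10 predictors, and at 10 coefficients on common levels divergence is essentially nil.
- The power gain comes from replacing Wald, not from Firth. LR on the ML fit is at least as powerful as Firth in every row, and at 10 coefficients its false-positive rate (4.8%-5.9%) hardly explains the difference.
- Firth does not reduce bias everywhere. For a true 2.0 in 27 lesions its median is 1.76 (12% low) against 2.18 for ML (9% high). In 38 lesions it is closer, 1.87 against 2.22.
- Merging levels with fewer than 20 lesions cuts divergence to 0%-2% without Firth.

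All of this stands. What remains is lower RMSE for common factors wherever it was examined, growing with the number of coefficients. Merging does not remove it: with levels under 20 merged, RMSE is still 0.198-0.216 for ML against 0.164-0.176 for Firth, and LR false positives stay at 5.9%-9.4%.

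**Conclusion.** This is a cheap improvement of modest priority, not a defect that invalidates the analysis. With 10 common-level coefficients ML is adequate (3%-8% exaggeration, about 7% higher precision from Firth). Two conditions make the change worthwhile:

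- Multi-level items enter as indicators. At 17-31 coefficients and 79% concordance, ML is 7%-21% too large and Firth RMSE is roughly 10%-25% lower.
- A small level is nearly always concordant while overall concordance is high. ML is then infinite in about 20% of datasets in the 38-lesion example, and Wald loses about 20-33 points of power for independent association.

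In the second case the difference between tests narrows at 65% concordance and disappears at 43%-50%, and it does not arise for levels with low concordance.

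Reading 10.3 as ordinary ML is an inference. Level counts, shares, effects, concordance and achieved N are assumptions, and the simulations treat lesions as independent.

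**What to change.** In 10.3, specify that the multivariable model is fitted by Firth penalised likelihood, with a penalised likelihood-ratio test for each factor and penalised profile-likelihood confidence intervals. If ML is kept, state at minimum that each factor is tested by likelihood ratio rather than Wald, and report the number of coefficients and the number of lesions in the smaller outcome class. That alone recovers the lost power.

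The cost is a few sentences of SAP wording and no new data. An SPSS extension or other software may be needed for one model; the documents do not settle this. Firth shrinks strong effects in sparse levels (median 1.76-1.87 for a true 2.0), and its test is somewhat less powerful than the ML likelihood-ratio test (90% against 93%, and 83% against 88%, in the examples above). It does nothing about several lesions from one patient being treated as independent under section 4; that needs separate handling.

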11.1 Compliance With Regulations and Standards

1. Investigators will implement quality control (QC) and quality assurance (QA) systems in accordance with standard operating procedures (SOPs).
2. Source documents must comply with relevant regulations and standards.
3. Laboratory test results must be accurate and reliable.
4. All observations and findings will be verified to ensure data reliability.
5. A complete study organizational structure will be established with clearly defined responsibilities at each level.
6. The principal investigator (PI) will be responsible for overall quality control and ensuring that all personnel fulfill their responsibilities.
7. The PI will be responsible for study protocol development and related documents; the PI will prepare the study summary report after study completion.
8. Designated personnel will develop the study implementation procedures and SOPs for use during the study.
9. Before study initiation, the study team will organize training on the protocol; all study personnel must receive GCP training.
10. Physicians and nurses participating in the study must strictly follow the protocol and procedures and must not modify them arbitrarily.
11. Designated statisticians will be responsible for comprehensive

statistical processing of the study data.

11.2 Protection of Participant Privacy

All participant data collected during the study will be entered into a computer system for confidential storage and analysis. If necessary, relevant authorities may audit the records to verify the authenticity, accuracy, and completeness of the data. Study results may be published in academic journals; however, participant names will not be disclosed, and participant privacy will be protected.

11.3 Problems During the Study and Corrective Measures

1. Protocol amendments: After ethics approval, any revision requires a “protocol amendment statement” signed by the PI. Amendments may be made only after consultation and agreement between the investigators and the sponsor (and/or the registration applicant, as applicable).
2. After revision, the amended protocol must be submitted to the ethics committee for review and approval prior to implementation.
3. No study personnel may deviate from the protocol.

11.4 Quality Control and Quality Assurance

11.4.1 Quality Assurance

The sponsor and any collaborating organizations entrusted by the sponsor with all or part of the study responsibilities shall establish their own QA systems, fulfill their responsibilities, and strictly adhere to the protocol and applicable SOPs to ensure the implementation of QC/QA systems.

11.4.2 Quality Assurance for Study Conduct

Prior to study initiation, investigators will receive training on the protocol to ensure full understanding of the study procedures and endpoints. QC personnel will verify basic study conditions to ensure that the site can meet protocol requirements. During the study, investigators will follow institutional SOPs and the protocol,

perform clinical procedures accordingly, and maintain true, timely, complete, and standardized records. QC personnel will review study processes and corresponding source documents. After study completion, study documents will be compiled, checked by QC personnel, and archived. The institutional QA department may conduct feasibility audits; when noncompliance is identified, investigators and responsible personnel will be notified to implement corrective actions and to track the completion of corrections.

11.4.3 Expected Study Timeline and Completion Dates

- October 2023 to January 2024: completion of data collection
- January 2024 to April 2024: completion of data analysis

11.5 Responsibilities of Each Party and Other Related Work

1. **Sponsor responsibilities:** The sponsor is responsible for initiating, applying for, and organizing this study, and for providing study funding.
2. **Investigator responsibilities:** Investigators will conduct the study in accordance with the Declaration of Helsinki and relevant regulatory, ethical, and scientific principles, and in accordance with the protocol. Investigators should be familiar with procedures and requirements for reporting serious adverse events (SAEs) and record/report such events as required. Investigators will enter data into study records accurately, completely, timely, and legally, and will accept monitoring/audits by sponsor- or CRO-appointed monitors/auditors and inspections by regulatory authorities to ensure study quality.
3. **Publication of study data:** The sponsor holds exclusive rights to the study data. Unless written permission is obtained from the sponsor or specified in a collaboration agreement, no publication should be made in an individual capacity prior to completion of the final report. The sponsor has final authority over manuscripts and publications.

11.6 Human Genetic Resources

The collection, acquisition, trade, export, or cross-border transfer of human genetic resources shall comply with the Interim Measures for the Administration of Human Genetic Resources (Guo Ban Fa [1998] No. 36).

12. Research-Related Ethics

12.1 Ethics Committee

Before study initiation, investigators must submit the investigator's brochure (if applicable), study protocol, request for waiver of informed consent, and any other participant-related information to the ethics committee for review and approval. Any protocol amendments must be approved again by the ethics committee.

12.2 Informed Consent

Qualified investigators must explain the nature and purpose of the study, procedures, expected duration, potential risks and benefits, and any possible discomfort to each participant as part of the informed consent process. Each participant must understand that participation is voluntary and that they may withdraw from the study at any time without affecting subsequent treatment or the relationship with their treating physician.

The informed consent form should follow a standard format and use non-technical language as much as possible. Each informed consent form must include the above content and a statement of voluntariness, and must be submitted to the ethics committee for approval.

A waiver of informed consent will be requested because study samples and information are derived from medical records and specimens collected during routine clinical care; the study poses no more than minimal risk; the waiver will not adversely affect participants' rights or welfare; and obtaining consent would make the study impracticable. Participant privacy and personal identifiers will be protected.

